### **Utilization Endpoints Analysis**

Utilization outcome will be calculated from the treatment parameters (intensity levels) and the treatment reports (usage of rescue medications), and will be presented in appropriate distribution tables.

Qualifies treatment was defined as

1 - Attacks treated with Nerivio for at least 20 minutes

2 - Pre and post treatment data were reported by the participant for the specific treatment

3 – No rescue medications were taken before and during the 2 hours post treatment, according to the participant report

Consistent efficacy will be conducted in cases where at least two qualified treatments were performed. Patients who experienced the outcome (e.g., pain freedom) in at least 50% of their reported treatments, during which they did not report the use of rescue medications, were considered responders.

Headache pain and functional disability will be rated at baseline and at 2 h post-treatment on a 4-point scale: severe, moderate, mild, or none. Migraine associated symptoms (photophobia, phonophobia, and nausea/vomiting) will be marked as present or not.

Pain relief will be calculated as a decrease from severe or moderate levels at baseline to mild or none at 2 h posttreatment.

Functional disability relief will be calculated as any improvement in disability from baseline to 2 h posttreatment.

Pain/functional disability freedom will be calculated as a decrease from any pain/disability level at baseline to none at 2 h post-treatment.

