**Study RWE-003**

Title	Real-World Evidence (RWE) of Usage of Nerivio, a Remote Electrical Neurostimulation (REN) Device In Adolescents Patients With Migraine
Sponsor	Theranica Bio-Electronics Ltd. [name]
Investigational Device	
Nerivio is a Remote Electrical Neuromodulation (REN) wearable, battery-powered medical device for the acute and/or preventive treatment of migraine with or without aura in patients 12 years of age or older. Nerivio is controlled by a mobile application. Nerivio is intended for self-administration in a home healthcare environment.
 
The device is worn on the upper arm and transmits transcutaneous remote electrical nerve stimulation by applying weak electrical pulses that invoke conditioned pain modulation (CPM) to inhibit migraine pain. Nerivio is intended for self-administration at the onset of a migraine episode.

Objectives	To evaluate the safety, utilization and efficacy of Nerivio in adolescent patients (Age 12-18) who used the Nerivio device for treating their migraine
Patient Population	Nerivio users aged 12-18 years old who registered a Nerivio account and used the Nerivio device for the acute treatment of migraine.
Sample size	The sample size will includes all Nerivio users in the age of 12-18 in the Nerivio database who treated with Nerivio at least once between Jan 01, 2021 and May 31, 2022
Inclusion criteria	

• Age between 12-18 years

• REN user across the United States who created Nerivio account on January 1st, 2021 until May 31, 2022.

• Had at least two evaluable treatments with the Nerivio device (for consistent efficacy analysis).

Exclusion criteria	

• Treatments shorter than 20 minutes will not be included in the analysis

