Study Design	
The analysis included patients at the age of 12-18 (at the day of opening a Nerivio account) with migraine across the USA who used Nerivio at least once between January 01, 2021, and May 31, 2022.
 
Treatment data will be collected through the Nerivio app (Nerivio®) which is required for treatment. Device output current is set by the user to be strong but not painful and is equivalent to treatment dosage (max device current 40 mA on 0-100 units user-facing scale). Additionally, patients can voluntarily log details about their symptoms at both treatment onset and 2-hours post-treatment status. Treatment efficacy will be measured by consistent reduction in headache pain intensity and functional disability at 2-hours post-treatment, based on data from patients who voluntarily will answer the pre and post treatment questionnaires. Safety will be assessed by the rate of device related adverse event reported by the patients.

Evaluable Treatment	
Evaluable treatment is a treatment that meets all the following criteria:
 

• Baseline and 2-hour post-treatment pain intensity and functional disability scores were recorded.

• The participant did not use any concomitant acute migraine medication during the treatment.

Efficacy endpoints	

1. Pain Relief: Reduction in pain intensity from moderate or severe (baseline score of 2 or 3) to mild or no pain (score of 1 or 0) at 2 hours post-treatment.

2. Pain Freedom: Reduction in pain intensity from mild, moderate, or severe (baseline score of 1, 2, or 3) to no pain (score of 0) at 2 hours post-treatment.

3. Functional Disability Relief: Reduction in functional disability by at least one point from baseline at 2 hours post-treatment.

4. Functional Disability Freedom: Reduction in functional disability from mild, moderate, or severe (baseline score of 1, 2, or 3) to no disability (score of 0) at 2 hours post-treatment.

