Utilization endpoints	

5. Consistent Usage of Migraine Abortive (Rescue) Medications: The proportion of subjects with REN treatments without the use of pharmacological migraine abortive (rescue) medication (either over the counter or prescribed), or with a combination of rescue medication or without any treatment at all at 2 hours post-treatment in at least 50% of all their treatments.

6. Treatment intensity distribution: The mean intensity of the stimulation collected for all treatments that were performed within the study

Safety endpoints	Rate of serious adverse events, adverse events and device-related adverse events

Data collection	
Data will be collected prospectively through the Nerivio smartphone application. At the time of creating a Nerivio account on the App, patients (and their parents, in case of patients younger than 18) are required to sign a consent statement presented to them, where they agree that their deidentified data may be collected and used for reserve purposes.
 
Prospective data was collected for Nerivio users in the United States who treated their migraine attacks with the Nerivio device. Nerivio utilization, and Nerivio treatment reports at T=0h and T=2h were extracted from the Nerivio server in an unidentified manner. Data will be analyzed per user following additional analysis per the target population.
 
The following data will be extracted:
 

• Demographics: Age at registration, gender.

• Treatment Details: Treatment date, baseline pain intensity, pain intensity at 2 hours post-treatment, baseline functional disability, functional disability at 2 hours post-treatment.

• Treatment Frequency: Number of treatments per month over the 12-months period.

• Pain Intensity: 0 (no pain), 1 (mild), 2 (moderate), 3 (severe).

• Functional Disability: 0 (no disability), 1 (mild interference), 2 (moderate interference), 3 (severe interference).

• Additional migraine symptoms (Nausea/ vomiting, Photophobia, Phonophobia)

Statistical considerations	See at the end of the document
Responder Definition	For each efficacy endpoint, a participants will be considered a responder if they achieved the defined outcome in at least 50% of their evaluable treatments during that study period.

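### The responder rate counts only users with two or more evaluable treatments, so it may overstate efficacy if read as the rate for all adolescents who used the device

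*Combined protocol and SAP*

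**What the plan says.** Efficacy is summarised by a per-user responder rate. Under Responder Definition in the synopsis, for each efficacy endpoint, "participants will be considered a responder if they achieved the defined outcome in at least 50% of their evaluable treatments". That sentence sets no minimum number of treatments. The minimum appears in two other places:

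- Inclusion criteria: "Had at least two evaluable treatments with the Nerivio device (for consistent efficacy analysis".
- Utilization Endpoints Analysis: "Consistent efficacy will be conducted in cases where at least two qualified treatments were performed".

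The population is described more widely. The Objectives speak of adolescents who used the device. The Sample size row takes in every user aged 12-18 "who treated with Nerivio at least once between Jan 01, 2021 and May 31, 2022", and Study Design repeats that scope.

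Whether a treatment counts depends on more than having taken place. Efficacy is "based on data from patients who voluntarily will answer the pre and post treatment questionnaires", and the statistical section also requires 20 minutes of treatment and "No rescue medications were taken before and during the 2 hours post treatment, according to the participant report". The synopsis term (evaluable) and the statistical section's term (qualified) are not defined identically; evaluable is used for both here.

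The only other efficacy analysis is a mixed model on treatment month (Efficacy Endpoints Analysis), with no population or minimum number of treatments stated. The plan has no first-treatment rate, no count of users with fewer than two evaluable treatments, and no sensitivity analysis that includes them.

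**The concern.** Entry to the responder set is settled after the first outcome is known. A user with one fully reported, medication-free treatment that failed belongs to the stated population and has an observed result, yet enters no responder proportion. If users without benefit are less likely to produce a second evaluable treatment, failures leave the denominator more often than successes do.

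The cohort has no control arm, and the hypothesis is that results resemble those in adults. A rate among users with repeated evaluable treatments is likely to be read as the rate in adolescents who used the device. Nothing planned would show how far apart the two are.

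**Working it through.** The plan gives no sample size, expected rate or share of users with one evaluable treatment, so it has no figure to reproduce. The rules come from the documents; every rate below is an assumption.

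**1. Who is left out.** All of these users belong to the at-least-once population but not to the responder rate:
- one evaluable treatment, a failure, no further use;
- one evaluable treatment, a success, no further attack or no further use;
- several treatments, of which fewer than two were reported, long enough and medication-free.

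**2. General size.** Among users with one or more evaluable treatments, let f be the share with exactly one, r1 their success rate, and R2 the responder rate in those with two or more. Then

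rate in all = (1 - f) × R2 + f × r1, and R2 minus that rate = f × (R2 - r1).

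With R2 = 0.60 and f = 0.30:

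| r1 | Rate in all | R2 minus rate in all |
|---|---|---|
| 0 | 0.42 | +0.18 |
| 0.40 | 0.54 | +0.06 |
| 0.60 | 0.60 | 0 |
| 0.80 | 0.66 | -0.06 |

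With r1 = 0, the rate in all is 0.54 at f = 0.10, 0.48 at f = 0.20 and 0.30 at f = 0.50. The sign depends only on whether r1 is below or above R2.

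**3. Selection on the first result.** Assume per-user success probability uniform on 0-1 (mean 0.50) and two treatments per continuing user. A fraction a continues after a success and c after a failure. The chance that the second treatment succeeds after a first failure is 1/3. In the two-treatment set:

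- first-treatment success = 0.5a / (0.5a + 0.5c);
- responder rate (one of two is enough) = (0.5a + 0.5c/3) / (0.5a + 0.5c).

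If everyone continues, the responder rate is 0.5 + 0.5/3 = 66.7%.

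| a | c | First-treatment success in set | Responder rate in set |
|---|---|---|---|
| 80% | 80% | 0.40/0.80 = 50% | 0.533/0.80 = 66.7% |
| 80% | 60% | 0.40/0.70 = 57.1% | 0.500/0.70 = 71.4% |
| 80% | 40% | 0.40/0.60 = 66.7% | 0.467/0.60 = 77.8% |
| 60% | 80% | 0.30/0.70 = 42.9% | 0.433/0.70 = 61.9% |

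The first-evaluable-treatment success rate in all users with one or more is 50% in every row, because it does not depend on a or c.

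**4. More treatments per user.** Simulation of 1,000,000 users, mean success 0.60 (Beta(1.2, 0.8)), five treatments per continuing user, single-treatment users counted by observed result:

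| Stop after failure / success | Two or more | All | Gap |
|---|---|---|---|
| 50% / 10% | 0.699 | 0.578 | +12 points |
| 40% / 20% | 0.662 | 0.597 | +6.5 points |
| 30% / 30% | 0.623 | 0.616 | +0.7 points |
| 10% / 50% | 0.537 | 0.655 | -12 points |

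**5. What adding single-treatment users can and cannot show.** Take the model in step 3 with 30% stopping whatever the result: 0.7 × 0.667 + 0.3 × 0.50 = 0.617. That is 5 points below 0.667 although stopping ignores the outcome, because one success in two is easier to reach than one in one. Adding only the single failures would be one-sided: at 80%/80% it gives 0.533/(0.80 + 0.10) = 59% against 67%.

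**The case against.** The strongest reply is that the estimand is declared. The endpoint is consistent efficacy, the minimum is stated openly and tied to that analysis, and consistency across attacks cannot be judged from one attack. This stands: the planned rate is valid for users with repeated evaluable treatments and should stay.

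Three stronger readings are tempting, and the documents do not support them.

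- A reader might infer that the rate is overstated and that the error favours the device. The documents give neither f nor r1 nor any continuation rate. The rule drops single successes as well as single failures, and step 4 runs from +12 to -12 points according to who stops.
- A reader might infer that a missing second evaluable treatment means the user gave up. The user may have treated again without reporting, with medication or for under 20 minutes, or may have opened the account shortly before the window closed on May 31, 2022.
- A reader might infer that every efficacy result excludes single-treatment users. The mixed model has no stated population, so this cannot be said. It compares treatment months, however, and does not supply an all-user rate.

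**Conclusion.** The point holds as a gap between the population described and the population analysed. The only stated user-level responder rate needs two evaluable treatments, the objective and sample cover users who treated once or more, and nothing planned would reveal the difference. The rate may be overstated as a description of all such users.

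Overstatement is the expected direction if users without benefit are less likely to provide a second evaluable treatment, which is plausible but undocumented. Under the step 3 assumptions it is about 5 points (71% against 67%) or 11 points (78% against 67%). It is nil with equal continuation and reversed if successes stop more often. These figures illustrate the mechanism and do not estimate the bias in this study. The change is worth making as a cheap improvement; the gap does not invalidate the planned analysis.

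**What to change.** - Keep the two-treatment responder rate under the consistent-efficacy label, and state that it applies only to users with repeated evaluable treatments.
- Beside it, for each endpoint, report the success rate of the first evaluable treatment in all users with one or more. This is the main addition: it treats successes and failures alike and removes the selection on having a second evaluable treatment.
- Give the number of users with 0, 1 and 2 or more evaluable treatments, and the success rate of those with exactly one.
- As a sensitivity analysis, add single-treatment users to the responder rate by their observed result, successes and failures alike. Note that part of any drop reflects the one-of-two threshold (step 5). If all of them are instead counted as non-responders, label that result explicitly as a lower bound.
- State the population of the mixed model.

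The cost is a few lines of SAP text and one table from data already to be extracted. The efficacy figure may be less favourable. Users with no evaluable treatment remain outside every rate, and a first evaluable treatment need not be the user's first treatment; the counts at least show how many users have none.
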